#### 3.0 PARTICIPANTS

This study involves recruiting EVD survivors and controls who have a clinical need for cataract surgery, which will be performed using the small incision cataract surgery technique which is standard practice in Liberia. Therefore, we will enroll all individuals who meet study eligibility criteria and would otherwise be eligible (clinically) to undergo cataract surgery.

The accrual ceiling is 120 people, with up to 60 EVD survivors and up to 60 controls. Current estimates of numbers of survivors and controls meeting eligibility criteria is lower, at about 35-45 survivors and 35 controls.

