# 9.1 Analysis of Data / Study Outcomes

If all PCR results and/or immunohistochemistry results are negative, simple models which assume independence across eyes from the same individual will be used to construct a 95% confidence interval for the probability of the aqueous humor being positive and/or the lenses being positive. If some results are positive, a more sophisticated approach will be used which recognizes the potential for an association in the outcome for eyes from the same individual. Since it is possible that some individuals receiving cataract surgery in both eyes will have discordant results, generalized estimating equations with a logistic link will be used to estimate the probability of testing positive given random effects for participants. This approach can be extended to accommodate tests for effects of age and gender (which are secondary outcomes).

Study CRFs capture the grade of anterior chamber cells for each eye according to the SUN criteria. Regression models will be fit with these grades as outcome variables and survivor status, age (less than 40 or greater than or equal to 40) and gender as explanatory variables. The test of the hypothesis of no difference in grade according to survivor status will be conducted by testing the null hypothesis that the regression coefficient associated with survivor status is zero. This will be conducted at the one and three month assessments. A significance level of 0.025 will be used for both tests to account for test multiplicity. These models will also allow for testing for the effects of gender and age, which is one of the secondary objectives. The secondary outcome about having 20/40 or better BCVA after surgery will be conducted using logistic regression with explanatory variables gender, age and survivor status.

To test for differences in postoperative structural changes after intraocular surgery between survivors and controls mixed effects models will be fit to data from the one month and three month exams for central subfield thickness and intraretinal fluid cysts. These models will also control for gender and age while testing for a difference due to survivor status. Linear models will be used for central subfield thickness and logistic regression models will be used for intraretinal fluid cysts. Tests of secondary outcomes will use a significance level of 0.05.

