To examine outcomes at the nine and 12 month exams, similar models will be fit but they will be extended to these later exams.

If less than 10% of participants have any cells observed in the anterior chamber, then the second primary outcome will be having cells detected (a dichotomous outcome) and the regression modeling strategy will be replaced with a logistic regression modeling approach.

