# 9.2 Power Analysis

We plan to enroll up to 120 participants of which 60 will be survivors and 60 contacts, to have cataract surgery as part of this protocol. The accrual ceiling is 120. If none of 40 samples test positive for Ebola RNA then a 95% confidence interval for the probability of testing positive will be (0.0, 0.09) indicating that we can conclude this occurs in less than 9% of cases. If 60 samples are obtained, then the 95% confidence interval for the probability of testing positive will be (0.0, 0.06) indicating that we can conclude this occurs in less than 6% of cases.

To examine the power for the association between survivor status and cell grade, we assume that we are just testing for a difference in the frequency with which anterior cells are observed in the two groups using Fisher's exact test. Results from PREVAIL III indicate that 10.4% of the eyes of survivors with cataracts have anterior chamber cells while only 0.4% of the eyes of contacts have cells observed. If we suppose that there are 60 participants in each group, then we have 38% power for detecting a difference using these two estimates (using a significance level of 0.025). If the rate among survivors is higher than this due to ongoing inflammation, then the power rapidly increases. Table 1 shows the power as it depends on the proportion of eyes with anterior chamber cells among survivors.

Table 1

Proportion	0.104	0.12	0.14	0.16	0.18
Power	0.38	0.52	0.69	0.81	0.89

**Table 1:** The power for the second primary aim using a dichotomous outcome. The proportion of eyes with cells among contacts is assumed to be 0.004 (the observed rate in PREVAIL III among contacts) while this proportion in survivors varies from 0.104 (the observed rate) to higher rates.

If participants do not follow instructions to take medication or return on the advised schedule, data will be analyzed using an intent-to-treat classification.

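### The logistic fallback for anterior chamber cells names no test and has no rule for a group with no events, which the plan's own rates make the most likely result

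*Combined protocol and SAP*

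**What the plan says.** Section 9.1 models the cell grade by regression with "survivor status, age (less than 40 or greater than or equal to 40) and gender as explanatory variables". The survivor comparison is made by "testing the null hypothesis that the regression coefficient associated with survivor status is zero", at a level of 0.025. On timing it says: "This will be conducted at the one and three month assessments".

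The fallback follows: "If less than 10% of participants have any cells observed in the anterior chamber", the outcome becomes "having cells detected (a dichotomous outcome) and the regression modeling strategy will be replaced with a logistic regression modeling approach". Nothing says whether the coefficient is tested by a Wald, likelihood-ratio, score, exact or penalised method, or what happens if one group has no cells. It is also not said at which visit or visits the 10% is counted. The rule in Section 9.1 for all-negative results concerns PCR and immunohistochemistry, not cells.

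Section 9.2 bases power on a difference in frequency "observed in the two groups using Fisher's exact test", with 60 per group, 10.4% of survivors' eyes and "only 0.4% of the eyes of contacts have cells observed". Section 3.0 expects actual numbers to be "lower, at about 35-45 survivors and 35 controls".

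**The concern.** Ordinary logistic regression has no finite survivor coefficient when all the events fall in one group. A control rate of 0.4% makes no events among 60 controls likely, and survivors with cells against no controls with cells is the pattern that most favours the study hypothesis. The standard error then explodes, and the default p-value comes out near 1 however many survivors have cells. The analyst would have to choose another method with the data in view, and the candidates do not agree at 0.025. At stake is the conclusion on the second primary outcome: power if the default output is accepted, and type I error if a convenient substitute is picked afterwards.

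**Working it through.** **Inputs.** Trigger below 10%, level 0.025, covariates age group and gender (Section 9.1). Rates 0.104 to 0.18 in survivors and 0.004 in controls, 60 per group (Section 9.2). Expected accrual 35–45 v 35 (Section 3.0). Tests are taken as two-sided; the plan does not say, but this reproduces its power table. One observation per participant, and the 10% counted at the visit being tested (assumption).

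**The plan's own figure.** Exact enumeration of two binomials with Fisher's test at 60/60 gives 0.374, 0.522, 0.685, 0.809 and 0.893. Table 1 states 0.38, 0.52, 0.69, 0.81 and 0.89. It is reproduced.

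**How often the fallback meets a group with no events.** At 60/60 the trigger means at most 11 participants with cells (11/120 = 9.2%; 12/120 = 10% does not qualify). No control events has probability 0.996^60 = 0.786. At 10.4% v 0.4% the fallback is triggered in 97% of trials. It is triggered with a group at zero in 77.1%. Taking out the trials with no events at all (0.896^60 × 0.786 = 0.001) leaves 77.0% with events in exactly one group. At 40/35 this is 82%. With the survivor rate kept at 10.4% and an assumed control rate of 2%, it is 29% at 60/60 and 47% at 40/35; with 5%, it is 5% at 60/60.

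**What each test does inside the fallback.** The trigger caps events at 11 (60/60), 7 (45/35 and 40/35) and 6 (35/35), so every possible table can be listed: 78, 36, 36 and 28 tables. Let a of n survivors and b of m controls have cells.

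- Wald: z = ln[a(m−b)/(b(n−a))] / √(1/a + 1/(n−a) + 1/b + 1/(m−b)). At 10/60 v 1/60, z = ln(11.8)/√1.137 = 2.31, p = 0.021. With b = 0 the estimate is infinite; a standard fit at 6/60 v 0/60 or 11/60 v 0/60 prints p = 0.999.
- Likelihood ratio at 6/60 v 0/60: 2 × (−19.505 + 23.822) = 8.63, p = 0.003.
- Fisher at the same table: 2 × C(60,6)/C(120,6) = 0.027.
- Firth (log-likelihood plus ½ log det of the information), penalised likelihood ratio at the same table: p = 0.011.

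Splits with more cells in survivors that reject at 0.025:

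| Test | 60/60 | 40/35 |
|---|---|---|
| Wald | 10 v 1 only | none |
| Fisher | 7 or more v 0; 9–10 v 1 | 7 v 0 |
| Firth | 5 or more v 0; 8–10 v 1 | 6–7 v 0 |
| Likelihood ratio | 4 or more v 0; 7–10 v 1; 9 v 2 | 4–7 v 0 |

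Wald also rejects for no split at 45/35 or 35/35. These rejection sets do not depend on the true rates. At 60/60 Firth and Fisher disagree at 5 v 0, 6 v 0 and 8 v 1.

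**Power of the whole rule, unadjusted.** When the fallback is not triggered, the analysis is taken as linear regression on cells coded 0/1 (assumption). The control rate is 0.004.

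| Sizes, survivor rate | Wald | Fisher | Firth |
|---|---|---|---|
| 60/60, 0.104 | 0.03 | 0.375 | 0.65 |
| 60/60, 0.18 | 0.45 | 0.90 | 0.96 |
| 40/35, 0.104 | 0.05 | 0.11 | 0.21 |
| 40/35, 0.18 | 0.43 | 0.57 | 0.71 |

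Of the Wald power at 60/60, only 0.009 and 0.025 come from the fallback. The rest comes from the linear branch.

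**Type I error at 60/60.** At a common rate of 5%, the ordinary likelihood-ratio test rejects in 0.043 of trials, Firth in 0.020 and Fisher in 0.004. Firth rejections from the fallback branch stay at or below 0.020 for null rates of 0.2% to 15%. The two-stage rule reaches 0.026 at 15%, with the excess coming from the linear branch.

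**With age and gender in the model.** In 4,000 simulated trials at each of three survivor rates (60/60; age and gender split 50/50, assumed), 7,737 triggered trials had a group with no events. Wald rejected in none of them (smallest p 0.993). Adjusted Firth size was 0.003–0.024 at 60/60 and 0.001–0.022 at 40/35 (null rates 2%–12%, age odds ratio 1 or 3, all assumed).

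**The case against.** The plan never mentions a Wald test. Its wording would also admit an exact, penalised or likelihood-ratio method. This stands: a reader might infer that the planned analysis can almost never reject, but the documents show only silence about the test. Even if Wald were used, power over the whole rule at a survivor rate of 0.18 is 0.45 at 60/60, because many such trials do not enter the fallback. With covariates, Wald can also reject a little more often (at 40/35, in at most 1.7% of trials in the settings simulated).

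The 77% and 82% rest on PREVAIL III per-eye rates. Every control eye analysed here has had surgery, and Section 1.1 expects a marked response in young patients. This also stands. At an assumed 15% v 5%, the one-group pattern falls to 4% (60/60) or 13% (40/35). At 25% v 5% the fallback is triggered in only 4% of trials at 60/60, and the choice hardly matters. Counting cells over several visits instead of one would also make the trigger rarer.

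A reader might infer that Table 1 is wrong. It is not: it is arithmetically correct, and Section 9.2 openly describes it as Fisher's test at 60 per group. Nor does Fisher's appearance there settle the analysis. It is introduced as a simplification for power, and it carries no age or gender term.

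Finally, Section 9.0 calls the sample sizes ones of convenience, and the protocol describes a natural history study. That accounts for modest power. It does not account for leaving a primary test open.

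**Conclusion.** The concern holds as a gap in specification with a real consequence. Read as ordinary logistic regression, the fallback has no finite survivor coefficient in about 77% of trials (60/60) or 82% (40/35) at the plan's own rates, and no other section supplies a rule. These percentages are conditional on rates from outside the post-operative setting and on a per-visit reading of the trigger. At 60/60 they fall to 29% or 5% if the control rate is 2% or 5%.

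Whatever the true rates, the reasonable candidates give different answers on the same table. The default one cannot reject, without adjustment, when a group has no events, and the ordinary likelihood-ratio test exceeds its level (0.043 against 0.025). At a survivor rate of 0.104 and 60/60, the choice moves unadjusted power from 0.03 to 0.65 among Wald, Fisher and Firth. The documents do not show that the sponsor intends a Wald test, or that the stated power is miscalculated. The method should be fixed before the data are seen.

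**What to change.** In Section 9.1, replace the ordinary logistic fallback with Firth penalised-likelihood logistic regression of presence of cells on survivor status, age group and gender. Use one operated study eye per participant (the first eye), since Section 4.3 allows second-eye surgery in some participants. Take the survivor-status p-value from the penalised likelihood-ratio test at 0.025, with a profile penalised-likelihood confidence interval, and state that Wald p-values are not used.

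State the visit or visits to which the 10% rule applies. Judging months 1 and 3 separately would match the two planned tests.

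Exact logistic regression would also handle a group with no events and keep the covariates. The essential point is that one valid method is named in advance.

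Table 1 needs no correction. A note that it is not the power of the adjusted test is optional.

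The cost is a few sentences and standard software, with no extra participants, visits or data. The downside is that the Firth estimate is slightly shrunk and must be reported as penalised.

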# 9.2 Power Analysis

We plan to enroll up to 120 participants of which 60 will be survivors and 60 contacts, to have cataract surgery as part of this protocol. The accrual ceiling is 120. If none of 40 samples test positive for Ebola RNA then a 95% confidence interval for the probability of testing positive will be (0.0, 0.09) indicating that we can conclude this occurs in less than 9% of cases. If 60 samples are obtained, then the 95% confidence interval for the probability of testing positive will be (0.0, 0.06) indicating that we can conclude this occurs in less than 6% of cases.

To examine the power for the association between survivor status and cell grade, we assume that we are just testing for a difference in the frequency with which anterior cells are observed in the two groups using Fisher's exact test. Results from PREVAIL III indicate that 10.4% of the eyes of survivors with cataracts have anterior chamber cells while only 0.4% of the eyes of contacts have cells observed. If we suppose that there are 60 participants in each group, then we have 38% power for detecting a difference using these two estimates (using a significance level of 0.025). If the rate among survivors is higher than this due to ongoing inflammation, then the power rapidly increases. Table 1 shows the power as it depends on the proportion of eyes with anterior chamber cells among survivors.

Table 1

Proportion	0.104	0.12	0.14	0.16	0.18
Power	0.38	0.52	0.69	0.81	0.89

**Table 1:** The power for the second primary aim using a dichotomous outcome. The proportion of eyes with cells among contacts is assumed to be 0.004 (the observed rate in PREVAIL III among contacts) while this proportion in survivors varies from 0.104 (the observed rate) to higher rates.

If participants do not follow instructions to take medication or return on the advised schedule, data will be analyzed using an intent-to-treat classification.

#### 10.0 HUMAN SUBJECTS PROTECTION

# 10.1 Equitability

Subjects enrolled on this study include all individuals who meet eligibility criteria and would otherwise be eligible (clinically) to undergo cataract surgery.

## 10.1.1 Justification for Exclusion of Children under 14 Years of Age

Children under 14 years of age are not eligible to enroll on this study because they would typically require general anesthesia for safe administration of cataract surgery, which is not being provided in this study.

# 10.1.2 Justification for Exclusion of Pregnant Women

Pregnant women are not eligible for this study because of the risk to the fetus for potential systemic absorption of medications such as anesthetic or oral steroids as no studies have yet demonstrated the safety of such drugs in fetuses. Cataract surgery is elective and waiting until after pregnancy is not expected to alter final surgical outcome.

# 10.1.3 Justification for Inclusion of Children over 14 Years of Age

Children over 14 years of age are eligible for this study as Ebola affects children and it is anticipated that children over age 14 will be to comply with the procedures required for this study; however, those who are unable to do so will be excluded.

## 10.1.4 Justification for Inclusion of Adults Who Cannot Consent

Adults who are unable to consent are eligible for enrollment because the study has the prospect for direct benefit and because data obtained from these individuals are necessary to answer important scientific questions about this disorder. Similarly, enrolled participants who lose the ability to provide ongoing consent during study participation may continue in the study.

# **10.2** Safeguards for Vulnerable Populations

Pregnancy testing will be performed at screening and one week prior to the cataract surgery. Participants with positive pregnancy tests will not proceed to the cataract surgery.

The study investigators have experience working with children and cognitively/decisionally impaired adults. A capacity assessment tool will be used to assess consent capacity, if capacity is in doubt (see Appendix 2). A pediatrician will be available for consultation if necessary.

Lactating women may enroll in this study. If steroids are needed to control inflammation in a lactating woman, then a steroid dosing schedule will be used to minimize effects to the breastfed child. Breastfeeding mothers will not be advised to stop or reduce breast feeding. The timing of steroids will be adjusted for nursing mothers to mitigate impact on nursing children.

#### 11.0 BENEFITS

EVD survivors without evidence of Ebola viral RNA in the aqueous humor will benefit from study participation by receiving cataract surgery under this protocol. Individuals who undergo cataract surgery typically experience a significant improvement in visual acuity and brightness. Cataract surgery is not routinely performed for EVD survivors because the RT-PCR technique used to assess presence of viral RNA is not routinely available in Liberia.

Controls will receive the benefit of cataract surgery on at least one eye, which they could also have outside of the study.

The knowledge gained in this study is expected to help guide ophthalmic surgical decisions made after EVD or possibly also other emerging infectious diseases.

#### 12.0 CONSENT DOCUMENTS AND PROCESS

The consent process follows the process which has been used for the other PREVAIL studies and is consistent with Liberian norms. This meets the criteria outlined in the Federal Policy Protection of Human Subjects Common Rule (45 CRF 46), understanding that NIH OHSRP SOP 20B, which describes NIH IRB responsibilities when reviewing local context considerations for offsite research, authorizes the NIH IRB to approve procedures that are adapted to local context.

The consent involves a two-step process consisting first of a group information session accompanied by the visual aids of a flip-book. All study details are discussed in detail and questions are answered in group format. This is followed by one-on-one consenting with a trained study team member. For this protocol, the entire consent language will be communicated to all potential participants verbally, so that illiterate and visually impaired potential participants receive the same information as everyone else being consented. This will be conducted in Liberian English, which is the local language. The informed consent form contains all required elements. This protocol has a standard consent form for all participants and an assent for participation of minors and individuals without consent capacity.

All participants will receive a verbal explanation in terms suited to their comprehension of the purposes, procedures and potential risks of the study. The participants must have the ability to understand and sign an informed consent form, which must be signed prior to enrollment. The participants will have an opportunity to carefully review the consent and ask questions regarding this study prior to signing, and they will be informed that they may withdraw from the study at any time without prejudice to themselves or benefits lost.

The investigator obtaining consent will document the consent process in the participant's medical record. A signed copy of the informed consent form will be provided to the participant to take home.

## 12.1 Consent Process for Illiterate Subjects

The process for obtaining informed consent from illiterate subjects is the two-step process described above which includes use of the visual aid flip-book and one-on-one consenting with the consent read out loud to participants in Liberian English.

# 12.2 Consent Process for Visually Impaired Subjects

Visually impaired subjects will participate in the same consenting process as other subjects which includes the opportunity to spend as much time as necessary to speak one-on-one with the study team member performing the consent who will read the consent out loud to participants in Liberian English and address all topics and questions.

#### 12.3 Consent Process for Minors

Consent for participation of minors will be obtained from parents/guardians (as determined by local Liberian law and custom. Written assent will be obtained from minor subjects.

The investigators will obtain consent from both parents if available, from one parent if the second parent is not available, or from a declared guardian when both parents are not available. This follows the process used in other PREVAIL protocols and approved by the Liberian Ethics Committee and respects Liberian norms for the consenting of minors.

If a pediatric participant reaches age of majority during the course of the study, study investigators with consenting privileges will re-consent the participant following the procedures for consenting adult participants.

# 12.4 Consent Process for Adults Without Consent Capacity

If during the one-on-one session, the consenting investigator determines the participant's capacity to consent is in question, a capacity assessment tool, the Study Understanding Evaluation Form (Appendix 2), will be used to assess the participant's capacity to consent. If participants successfully answer all questions, consent will proceed per usual. In the event that a potential participant cannot answer all questions, they will be determined to not have the capacity to consent for themselves at that time. Once lack of capacity has been determined, an attempt will be made to find a guardian, as determined by local Liberian law and custom, who can consent on their behalf. If no guardian can be identified, then that individual will not be enrolled in the study. By way of additional background, all adult participants enrolled to date on PREVAIL protocols have had the capacity to consent, and no adults have been declined enrollment in PREVAIL protocols to date for lack of capacity to consent.

